### **8.7. Immunogenicity Assessments**

Antibodies to JNJ-77242113 will be evaluated in serum samples collected from all participants according to the SoA, Section 1.3. Additionally, serum samples should also be collected at the final visit from participants who discontinued study intervention or were withdrawn from the study. These samples will be tested by the sponsor or sponsor's designee.

Serum samples will be screened for antibodies binding to JNJ-77242113 and the titer of confirmed positive samples will be reported. Other analyses may be performed to verify the stability of antibodies to JNJ-77242113 and/or further characterize the immunogenicity of JNJ-77242113.

Serum samples will be used to evaluate the immunogenicity of anti-JNJ-77242113 antibodies. Samples collected for immunogenicity analyses may additionally be used to evaluate safety or efficacy aspects that address concerns arising during or after the study period. Genetic analyses will not be performed on these serum samples. Participant confidentiality will be maintained.

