### 9.3. Populations for Analysis Sets

For the efficacy analyses in this study, the full analysis set (FAS) will be used according to the participants' assigned treatment to which they were randomized, regardless of the treatment they received. The FAS includes all randomized participants who receive at least 1 administration of study intervention. The FAS will be used for all primary and secondary efficacy analyses.

Safety analyses will include all randomized participants who received at least 1 administration of study intervention and participants will be analyzed based on the treatment they actually received,

regardless of the treatment groups to which they were assigned. Pharmacokinetics analyses for JNJ-77242113 will include all randomized participants who receive at least 1 complete dose of JNJ-77242113 CCI and have at least 1 valid blood sample drawn for PK analysis after their first dose of JNJ-77242113 CCI. Antibodies to JNJ-77242113 will be analyzed for all randomized participants who receive at least 1 dose of JNJ-77242113 CCI and have at least 1 sample obtained after the first dose of JNJ-77242113 CCI for the detection of antibodies to JNJ-77242113.

For purposes of analysis, the following populations are defined:

Population	Description
Enrolled	All participants who sign the ICF.
Randomized	All participants who were randomized in the study.
FAS	All randomized participants who take at least 1 dose of study intervention.
Safety Analysis Set	All randomized participants who take at least 1 dose of study intervention.
PK Analysis Set	All randomized participants who take at least 1 complete dose of study intervention and had at least 1 valid blood sample drawn for PK analysis after their first dose of study intervention.
Immunogenicity Analysis Set	All randomized participants who take at least 1 complete dose of study intervention and had at least 1 sample obtained after their first dose of study intervention.

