| To explore treatment effects of an oral tablet formulation of JNJ-77242113 on biomarkers in participants with moderate-to-severe plaque psoriasis.  | 
 
• Change from baseline in levels of skin and blood biomarkers.
 
   |
| To evaluate the immunogenicity of JNJ-77242113.   | 
 
• The incidence of anti-drug antibodies to JNJ-77242113.
 
   |
| To further assess the safety and tolerability of an oral tablet formulation of JNJ-77242113 compared with placebo in participants with moderate-to-severe plaque psoriasis.   | 
 
• Frequency and type of AEs, SAEs, reasonably related AEs, and AEs leading to discontinuation of study intervention.
 
• Laboratory parameters and change from baseline in laboratory parameters (hematology and chemistry) over time.
 
• Systolic and diastolic blood pressures over time.
 
   |
| To evaluate the treatment effect of an oral tablet formulation of JNJ-77242113 on patient-reported psoriasis severity and dermatology-specific health-related quality of life compared with placebo in participants with moderate-to-severe plaque psoriasis.                 | 
 
• Change from baseline in Psoriasis Symptoms and Signs Diary (PSSD) symptoms score at Week 16.
 
• Change from baseline in PSSD signs score at Week 16.
 
• Proportion of participants achieving a PSSD symptoms score=0 at Week 16 among participants with a baseline symptom score <math>\geq 1</math>.
 
• Proportion of participants achieving a PSSD signs score=0 at Week 16 among participants with baseline sign scores <math>\geq 1</math>.
 
• Proportion of participants achieving a Dermatological Life Quality Index (DLQI) score of 0 or 1 at Week 16 among participants with baseline DLQI score <math>> 1</math>.
 
 |

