**Table 1: Populations for Analyses**

| Population                  | Description   |
|-----------------------------|---|
| Enrolled                    | All participants who signed the ICF   |
| Randomized                  | All participants who were randomized in the study   |
| FAS                         | All randomized participants who took at least 1 dose of study intervention  |
| Per Protocol (PP)           | The per protocol analysis set (PP) includes a subset of participants in the full analysis set (FAS) who were in compliance with the protocol. Compliance is defined as participants in FAS and meet the following criteria: 
 
Has a total BSA <math>\geq 10\%</math> at the screening and baseline visit.
 
Has a total PASI score <math>\geq 12</math> at the screening and baseline visit
 
Has a total IGA score <math>\geq 3</math> at the screening and baseline visit
 
Overall compliance of study treatment at least 80% prior to Week 16, Or participants who did not complete all scheduled study intervention administration due to intercurrent events (i.e., discontinued the study intervention due to lack of efficacy, an AE of worsening of psoriasis, or started a protocol-prohibited medication or therapy during the study that could improve psoriasis)
 
Criteria added as needed after the team's review.
 
 |
| Safety Analysis Set         | All randomized participants who took at least 1 dose of study intervention  |
| PK Analysis Set             | All randomized participants who received at least 1 dose of JNJ-77242113 CCI and had at least 1 valid blood sample drawn for PK analysis after their first dose of JNJ-77242113 CCI   |
| Immunogenicity Analysis Set | All randomized participants who received at least 1 dose of JNJ-77242113 CCI and who had at least 1 sample obtained after the first dose of JNJ-77242113 for the detection of antibodies to JNJ-77242113  |
| PD Analysis Set             | All randomized participants who received at least 1 dose of JNJ-77242113  |

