## 5.7.2. Immunogenicity

### 5.7.2.1. Antibodies to JNJ-77242113

Immune response analyses will be based on the Immunogenicity Analysis Set.

The incidence and titers of antibodies to JNJ-77242113 will be summarized for all participants who receive at least 1 dose of JNJ-77242113 and have appropriate samples for detection of antibodies to JNJ-77242113 (ie, participants with at least 1 sample obtained after their first dose of JNJ-77242113).

The antibody to JNJ-77242113 status (positive at any time, negative) and titers will be summarized by treatment group for participants who receive a dose of JNJ-77242113 and have appropriate samples for detection of antibodies to JNJ-77242113 (ie, participants with at least 1 sample obtained after their first dose of JNJ-77242113).

Participants evaluable for immunogenicity are defined as having at least 1 dose of JNJ-77242113 and have at least 1 valid blood sample drawn for antibody detection. The antibodies to JNJ-

77242113 summary and analysis will be based on the observed data; therefore, no imputation of missing data will be performed.

The following analysis of antibodies to JNJ-77242113 will be performed by treatment group:

- Summary of incidence of antibody to JNJ-77242113 status
- Summary of neutralizing antibodies (NAb) to JNJ-77242113

A listing of participants who are positive for antibodies to JNJ-77242113 will be provided. The sample antibody status, the titer, and the neutralizing antibody status to JNJ-77242113 will be listed by visit. This listing will also provide information regarding dose administered, JNJ-77242113 plasma concentration, PASI score, PASI75 response status, and IGA 0/1 response status for all applicable visits. In addition, a list of antibodies to JNJ-77242113 status in participants who discontinued study agent early will be provided.

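### Antibody samples are evaluated in all arms, but the SAP summarizes them for JNJ-77242113 recipients only, leaving ADA incidence with no concurrent placebo rate and no stated comparison with Week 0

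*SAP*

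**What the plan says.** Collection covers everyone. Protocol 8.7 states: "Antibodies to JNJ-77242113 will be evaluated in serum samples collected from all participants according to the SoA". The Schedule of Activities (protocol 1.3) lists the sample at Weeks 0, 2, 4, 8, 16 and 20 and at early termination. Its footnotes place all Week 0 sampling before the first dose.

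The analysis does not cover everyone. SAP Table 1 opens its definition of the Immunogenicity Analysis Set with "All randomized participants who received at least 1 dose of JNJ-77242113 CCI and who had at least 1 sample"; the sampling condition in full is "and who had at least 1 sample obtained after the first dose of JNJ-77242113 for the detection of antibodies to JNJ-77242113". SAP 5.7.2.1 adds: "Immune response analyses will be based on the Immunogenicity Analysis Set". It then specifies the outcome: "The antibody to JNJ-77242113 status (positive at any time, negative) and titers will be summarized by treatment group". The exploratory endpoint in SAP 1.1 is "The incidence of anti-drug antibodies to JNJ-77242113".

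The protocol is not consistent about the set. The text of 9.3 reads: "Antibodies to JNJ-77242113 will be analyzed for all randomized participants who receive at least 1 dose of JNJ-77242113 CCI". The table in the same section instead requires at least one "complete dose of study intervention and had at least 1 sample obtained after their first dose of study intervention", which takes in placebo. Protocol 9.4.6 opens with study intervention and narrows to JNJ-77242113 in a parenthesis. SAP Appendix 2, which should record departures from the protocol's planned analyses, is marked not applicable.

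**The concern.** A placebo-controlled trial collects antibody data in its control arm and then plans no summary of them. ADA status is counted as ever positive across repeated samples, and such a count rises with the number of samples even if the drug does nothing. The SAP gives no treatment-emergent definition and does not say how a participant already positive at Week 0 is to be classified. A small number of positives among active participants would therefore be reported without either of the two reference points the trial already collects: the same participants before dosing, and placebo participants sampled on the same schedule. Protocol 2.3.1 lists ADA production among the potential risks of the study intervention, so some reader will have to interpret that number.

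**Working it through.** **1. Who is counted.** SAP 1.2 gives 3:3:2 allocation of 80, stated as 30:30:20. This reproduces: 80 × 3/8 = 30, 30, and 80 × 2/8 = 20. Under SAP Table 1 the set holds at most 30 + 30 = 60, so 20 of 80 (25%) are left out. The documents give no expected ADA rate and no precision target.

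**2. The definitions side by side.**
- Protocol 9.3 text: at least one dose of JNJ-77242113 and a later sample. Placebo out.
- Protocol 9.3 table: at least one complete dose of study intervention and a later sample. Placebo in.
- Protocol 9.4.6: study intervention first, then JNJ-77242113. Unclear.
- SAP Table 1 and 5.7.2.1: at least one dose of JNJ-77242113. Placebo out.

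The SAP matches the protocol text but not the protocol table. The table also asks for a complete dose, which the text and SAP Table 1 do not.

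**3. What Week 0 offers.** It gives a pre-dose reading in every arm. With no positives among n participants, the exact two-sided 95% upper limit is 1 − 0.025^(1/n):
- n = 60 (active arms): 6.0%
- n = 80 (all arms): 4.5%
- n = 20 (placebo alone): 16.8%

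For reactivity in a single sample, Week 0 is therefore the more precise source.

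**4. Why Week 0 is not the whole answer.** There are five scheduled post-dose samples (Weeks 2, 4, 8, 16, 20). Let f be the chance that one sample is a confirmed false positive. This rate is an assumption and is not in the documents. If samples are independent, the chance of at least one positive is 1 − (1 − f)^5.

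| f | ever positive post-dose | expected of 60 active | expected of 20 placebo |
|---|---|---|---|
| 0.5% | 2.5% | 1.5 | 0.5 |
| 1% | 4.9% | 2.9 | 1.0 |
| 2% | 9.6% | 5.8 | 1.9 |

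At f = 1%, Week 0 would show about 1% while the ever-positive count would show 4.9%. Independence is the upper end here. If the same people react at every visit, the cumulative figure falls back toward f. Where it lies between the two is not known from the documents, and only participants sampled repeatedly without drug show it directly.

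**5. What 20 placebo participants can show.** Over 20 × 5 = 100 samples the chance of no placebo positive is (1 − f)^100: 61% at f = 0.5%, 37% at 1%, 13% at 2%. The 16.8% upper limit for 0 of 20 lies above the whole 2.5% to 9.6% range in step 4. The column is useful as description, not as a test.

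**The case against.** A reader might infer that the trial has no background rate at all and so cannot separate drug-induced antibodies from assay reactivity. The documents do not support that. A pre-dose sample is scheduled for every participant, positives are confirmed before a titer is reported (protocol 8.7), the assay is to be validated, and SAP 5.7.2.1 lists antibody status by visit for positive participants. Background reactivity can be estimated from data in hand, and in the active arms more tightly than from placebo.

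A reader might also take the protocol 9.3 table as proof that placebo was meant to be included. That is weak evidence: the same table defines the PK set by study intervention, where placebo recipients would make little sense, so the wording may be generic.

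Nor does the immunogenicity objective say that the comparison is with placebo, unlike the efficacy and safety objectives. Describing incidence among exposed participants is a fair reading of it. And with 20 participants, a placebo column often could not settle whether a low active-arm rate is due to the drug.

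All of this stands and narrows the point. Two things remain. The SAP does not state any use of Week 0 in classifying ADA status, so the background information available is not applied. And a single pre-dose sample does not measure the same quantity as an ever-positive count over five post-dose samples, which the placebo arm does.

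**Conclusion.** The point holds in a limited form. ADA results exist for all arms, but the planned summaries leave out the 20 placebo participants, so the ever-positive incidence is given without a concurrent rate and without a stated comparison with Week 0. The protocol's definitions of the set conflict, and the SAP does not record which was followed.

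The size is small. The endpoint is exploratory and descriptive, and the primary conclusion is unaffected. The 2.5% to 9.6% background range rests entirely on assumed false-positive rates of 0.5% to 2% per sample and on independence across five samples. Within-participant correlation would lower it. The documents give no such rate and no expected true incidence, so they do not support a claim that the reported incidence will be mostly background.

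**What to change.** - Reconcile the set across the protocol 9.3 text and table, protocol 9.4.6, SAP Table 1 and SAP 5.7.2.1, including whether a complete dose is required. Record any departure from the protocol in SAP Appendix 2.
- For the descriptive ADA incidence, titer and neutralizing-antibody summaries, define the set by study intervention plus at least one post-dose sample, and show placebo as a column.
- Report post-dose positivity separately from Week 0 positivity, and state how participants positive at Week 0 are classified.
- Keep the antibody-versus-PK and antibody-versus-efficacy analyses on the active arms.

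The cost is a few edits to definitions and one table column, using samples already planned for collection and evaluation in every arm. The drawbacks are that any placebo positives will need a comment, and that the placebo rate must be presented with its interval so that 0 of 20 is not read as proof of no background.

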## 5. STATISTICAL ANALYSES

### 5.1. General Considerations

Unless specified otherwise, efficacy data summaries will be provided by intervention group for FAS. Data primarily will be summarized using descriptive statistics. Continuous variables will be summarized using the number of observations, mean, SD, median, interquartile range, minimum and maximum, as appropriate. Categorical values will be summarized using the number of observations and percentages as appropriate. In addition, graphical data displays (eg, line plots) and participant listings may also be used to summarize/present the data.

For binary response efficacy endpoints, comparisons between each of the JNJ-77242113 CCI groups versus placebo will be performed using a Cochran-Mantel-Haenszel (CMH) test stratified by the baseline weight ( $\leq 90$  kg,  $>90$  kg). For continuous efficacy endpoints, treatment comparisons will be performed using a Mixed-Effect Model Repeated Measure (MMRM) model. The MMRM model will have factors for treatment group, baseline weight ( $\leq 90$  kg,  $>90$  kg), baseline value for the corresponding efficacy endpoint, visit, and treatment group by visit interaction. An unrestricted (UN) variance-covariance matrix for repeated measures within a participant will be used. If the model with unstructured covariance structure does not converge, alternative covariance structures

will be considered in the following order, with the first structure that converges being used in the analysis: heterogeneous Toeplitz, standard Toeplitz, and autoregressive of order 1.

The Least Square mean (LSmean) estimates and their corresponding 90% confidence interval (CI) will be provided at each time point. In addition, the estimates of LSmean difference and 90% CIs between the JNJ-77242113 groups and placebo will be provided.

In general, all statistical tests will be performed at a 2-sided significance level of  $\alpha=0.10$ . Nominal p-values will be reported. No multiplicity adjustment is planned for this phase 2a proof-of-concept study.

The baseline measurement is defined as the closest measurement taken prior to or at the time of the first study agent administration date unless otherwise specified.

### 5.1.1. Visit Windows

The schedules for visits of the study will follow per protocol 'Schedule of Activities' table. Visits at Week 1 and Week 2 should occur within  $\pm 2$  days of the scheduled visit; and the visits after Week 2 through Week 16 should occur within  $\pm 4$  days of the scheduled visit. The final follow-up visit (ie, Week 20) should occur approximately 4 weeks after the last administration of study intervention.

Nominal visits of Week 0 through Week 16 will be used for all by visit analyses. Visit windows will be created around the study day of each scheduled visit and be applied to map early termination visit and final follow-up visit. The visit windows and the targeted study day are indicated in Table 1. Scheduled visit assessments are preferred if more than one assessment falls within the same visit window.

Table 1. Visit Windows

| Scheduled Study Day   | Visit Window |
|---|--------------|
| Week 0 Day 1*   | 1, 4         |
| Week 1 (Day 8)  | 5, 11        |
| Week 2 (Day 15)   | 12, 21       |
| Week 4 (Day 29)   | 22, 42       |
| Week 8 (Day 57)   | 43, 70       |
| Week 12 (Day 85)  | 71, 98       |
| Week 16 (Day 113)   | 99, 126      |
| Week 20/Final Follow-up   | 127, 999     |
| * Study Day 1 begins on the day of randomization. Each Week consists of 7 days. |              |

### 5.1.2. Reference Date, Study Day and Relative Day

The Reference Date is the date of the first study agent administration. If the date of the first study agent administration is missing or the first study agent administration is not done, then the Reference Date equals the corresponding visit date (eg, Week 0 visit date). If the corresponding visit date is also missing, then the Reference Date equals the randomization date. Study day is

defined as the number of days from the study reference date to the event/visit date. It will be calculated as follows:

- If the event/assessment occurs on or after the reference date, then study day = event/assessment date – reference date + 1.
- If the event/assessment occurs before the reference date, then study day = event/assessment date – reference date.

Hence, the day of reference date is Study Day 1; the previous day is Study Day -1.

### 5.1.3. Treatment Groups

In the efficacy analyses, FAS will be used, and the participants will be analyzed according to the randomized treatment groups they were assigned to, regardless of the treatments they actually received. Unless otherwise specified, efficacy analyses for placebo comparisons at Week 16 or through Week 16 will be summarized and displayed as follows:

- **Placebo:** Participants randomized to placebo group at Week 0.
- **10 mg JNJ-77242113 oral delayed release tablet** CCI [REDACTED] Participants randomized to 10 mg group CCI [REDACTED] at Week 0.
- **50 mg JNJ-77242113 oral delayed release tablet** CCI [REDACTED] Participants randomized to 50 mg group CCI [REDACTED] at Week 0.

### 5.2. Participant Dispositions

The number of screened participants will be summarized overall.

The number of participants in the following disposition categories will be summarized throughout the study by intervention group and overall:

- Participants randomized
- Participants who received study intervention
- Participants who completed the study
- Participants who discontinued study intervention
  - Reasons for discontinuation of study intervention
- Participants who terminated study prematurely
  - Reasons for termination of study

Listings of participants will be provided for the following categories:

- Participants who discontinued study intervention
- Participants who terminated study prematurely
- Participants who were unblinded during the study period
- Participants who were randomized yet did not receive study intervention.
- Participants who were randomized with incorrect stratum.

The above categories will include summaries over the placebo-controlled period through Week 16.

### **5.3. Primary Endpoint Analysis**

#### **5.3.1. Definition of Primary Endpoints**

The primary efficacy endpoint is the proportion of participants achieving PASI 75 response at Week 16, defined as at least a 75% reduction from baseline in PASI total score.

The PASI is a system used for assessing and grading the severity of psoriatic lesions and their response to therapy. In the PASI system, the body is divided into 4 regions: the head, trunk, upper extremities, and lower extremities which account for 10%, 30%, 20%, and 40% of the total BSA, respectively. Each of these areas is assessed separately for erythema, induration, and scaling, which are each rated on a scale of 0 to 4; and the area of involvement for psoriatic lesion is rated on a scale of 0 (no involvement) to 6 (90% to 100% involvement) The PASI produces a numeric score that can range from 0 (no psoriasis) to 72. A higher score indicates more severe disease.

Efficacy endpoints related to the PASI score are defined below:

